Title Page

Title: Safety Education in the Emergency Department: A Pilot Study

Identifier: NCT05168878

Document date: April 17, 2020

COMIRB Protocol

COLORADO MULTIPLE INSTITUTIONAL REVIEW BOARD

[name] [contact] [contact]

Protocol #: 20-0238

Project Title: Safety Education in the Emergency Department (SEED): A pilot study

Principal Investigator: [name]

Version Date: 04/17/2020

I. Hypothesis and specific aims

The goal of this proposal is to determine the feasibility and acceptability of using a video in the Emergency Department (ED) at the Children's Hospital Colorado (CHCO) to promote the safe storage of firearms, and safe firearm behaviors, in homes with children. We also intend to obtain pilot data to evaluate parental storage practices and knowledge surrounding temporary firearm transfer out of the home in times of crisis and determine whether these can be improved following a standardized ED intervention. Our overall hypothesis is that presenting a video during a child's ED stay will improve communication with the ED provider ultimately increasing safe firearm storage. In order to test this hypothesis, we are proposing a pilot study to test the feasibility, acceptability and effectiveness of a video intervention in the ED with the following aims:

Aim 1: Aim 1: Evaluate the effectiveness of safe firearm storage education for medical and surgical patients in the Children's Hospital Colorado (CHCO) ED by measuring change in self-reported safe storage at baseline and 3 months after a brief ED intervention.

Hypothesis: Safe storage counselling will improve safe storage practices by 15% over baseline rates, as measured by removing all guns from home or locking all guns and locking ammunition separately.

Aim 2: Evaluate the effectiveness of a brief ED intervention in improving parental knowledge surrounding temporary firearm transfer out of the home as a lethal means restriction strategy by measuring parental knowledge at baseline and 3 months after a brief ED intervention.

Hypothesis: Parents will not be aware of temporary firearm storage as a lethal means restriction strategy, and an ED intervention will be effective at improving this knowledge.

Aim 3: Compare the feasibility of having parents watch a short, 30-second, to a long, 3-minute, Be SMART firearm safety video in the CHCO ED.

Hypothesis: We believe that at least 10% more parents will complete watching the 30 second video compared with the 3-minute video as measured by data retrieved from the GetWell network.

Aim 4: Evaluate the acceptability of both videos to parents who view the video with a post-test survey administered in the ED using a survey modified from previous work done at our institution [1].

Hypothesis: We expect that the video will be acceptable to 75% of parents who view the video.

Aim 5: Assess the number of parents that participate in a follow up survey within 3 months after the ED visit.

Hypothesis: We hypothesize that 65% of parents will complete the entire follow-up survey.

This study is the first step in determining if offering a firearm safety video focused on safe storage in the ED is feasible and acceptable to our parents, and whether it is effective in a subset of families with older children known to have firearms in the home. The results generated from this study will lead to evaluating the effectiveness of the video at changing firearm storage and safety behaviors among a larger population of families. Given that we see 75,000 patients annually in our ED, we have the infrastructure in place to test this pilot study and future interventions. If effective, we also have the infrastructure to support broad implementation, including to our network sites, reaching a sizable and diverse population of Colorado families.

II. Background and significance

Firearm injuries, both intentional and unintentional, are a public health crisis in the United States. Among children and adolescents nationally, firearm related injuries are the second leading cause of death, accounting for more than 15% of all fatalities in individuals age 1-19 years old, and [2]. The intent of injury varies with age, with 26% of firearm deaths among children (1-9 years old) being unintentional [2]. In contrast, among adolescents (10-19 years old), nearly all deaths - 97% - were intentional with 39% due to suicide [2]. Suicide is of even greater concern in Colorado, which is the state with the 10th highest suicide rate in the country with a rate of 20 suicide deaths per 100,000 population, well above the national average of 14 per 100,000 [3].

The American Academy of Pediatrics (AAP) recommends storing firearms locked, unloaded, and separate from ammunition [4]. Each of these measures has proven protective against unintentional injuries and suicide by firearm in youth [5]. This effect on suicide *attempt* by firearm is critical as the use of lethal means plays a crucial role in whether an individual completes suicide [6]. Firearms are the most lethal means of suicide with a fatality rate of 90% [7], accounting for 54% of suicide deaths even though they were used in only 6% of attempts [8].

Firearms are *only safely stored in one third of homes with children* [9, 10]. This, despite most unintentional injuries being caused by a gun found in the home [11], and evidence that children cannot be “taught” firearm safety at a young age, playing with guns even when warned not to [12]. There is no improvement in storage practices in homes of children who are at higher risk for suicide [13]. Easy availability of firearms in the home correlates significantly with adolescent suicide rates, with 80% of youth suicides occurring in their home, most commonly with a parent’s firearm [14]. In most of *these* cases, the firearms were not stored per recommended safe storage practices [5].

Improving rates of safe storage in homes with children and adolescents, thus decreasing access to firearms for this age group, is essential to decreasing firearm morbidity and mortality. The challenge lies in identifying the best mode and setting by which to communicate this to families. The ED is uniquely positioned to reach a broad population with an educational intervention. Pediatricians are excellent candidates to deliver this safety message as child health advocates, and do so effectively in the primary

care setting [15]. This message is also effective in the ED for patients who require evaluation for active suicidality. In this context, a five-minute intervention by a psychiatrist and provision of a lockbox proved effective at improving safe firearm storage and decreasing access to lethal means in patients at high-risk for suicide [1].

The aspect of the ED which makes it an excellent setting, in that patients are primed for safety education and providers are natural advocates, also presents challenges. Generally, providers spend less time with the patient and the physician-patient relationship is not as well developed as in primary care. In addition, ED resources are inadequate and providers too numerous to generalize in-person counselling.

Video-based patient education is effective in engaging and educating patients in other settings and topic areas [16], and is frequently used at CHCO to educate families about medical diagnoses or child safety. We expect an educational video to be an effective mechanism to provide firearm safety education in the ED as it is brief, reproducible, and obviates the need to train providers or utilize additional provider time.

The Be SMART campaign , developed by Everytown for Gun Safety, has developed firearm safety videos based on their messaging of “Secure all guns in your home and vehicle, Model responsible behavior, Ask about the presence of unsecured guns in other homes, Recognize the role of guns in suicide, Tell your peers to be SMART” [17] – one 30-second video and a second 3-minute video. This framework is applicable to individuals regardless of firearm ownership. It is currently being studied as an educational model at a small number of pediatric inpatient units and primary care settings across the country. We do not know, however, if it is feasible to show these videos to parents of patients presenting to the ED, if the messaging will be acceptable in our population, or if they are an effective means of changing behavior.

We intend to address a portion of this knowledge gap with this pilot study to demonstrate the feasibility of 1) showing the video in the ED and 2) whether parents will participate in a 3-month up phone call to evaluate for improvement in safe firearm behaviors. We will evaluate the acceptability of the video using a modified version of a survey previously used at our institution [1]. In a subset of the population who are firearm owners, thus at higher risk, we will collect pilot data to understand whether this video, coupled with a handout, appears to be effective. If feasible and acceptable, we will seek to evaluate the effectiveness of the video, and compare the effectiveness of the two videos, via a randomized control trial.

III. Research Methods

A. Outcome Measure(s):

Specific aims 1 and 2:

Primary outcome measures:

- 1) Safe firearm storage will be measured by self- report based on the survey questions such as, “Are any of the guns in your home kept unlocked?”, and “Are the bullets stored separately from the guns?”.
2) Parental awareness of temporary firearm transfer will be measured by self-report based on questions such as, “Did you know that you can temporarily take your guns out of your home if you are concerned that someone in your house may hurt themselves or someone else?”.
Responses answers are yes or no.
3) Parental knowledge of temporary firearm storage options will be measured by the ability to name at least one location for temporary firearm storage OR describe the link for a map of storage locations.

Specific aims 1-5:

- 4) Feasibility of delivering the intervention in the Emergency Department (ED) measured by
 - a. Proportion of caregivers approached who agree to participate in the study.
 - b. Proportion of caregivers who complete the video in its entirety, based on data provided by the GetWell network who will be hosting the video content.
 - c. Proportion of caregivers who complete the baseline survey, which will ask questions about general child safety behaviors, current firearm storage, acceptability of video content and acceptability of showing the video during the ED visit.
- 5) Acceptability of the educational videos as measured using a survey at baseline with primarily closed-ended questions such as "How useful was the information you received?" and "Was the information you received confusing?". There will also be an open-ended question to solicit additional feedback
- 6) Feasibility of completing a follow up survey with parents within 3 months after the intervention measured by the proportion of caregivers who complete the survey in its entirety either electronically or by phone.

B. Description of Population to be Enrolled:**Inclusion criteria:**

1. Children > 30 days and < 18 years old presenting to the CHCO ED
2. Parent/guardian who is ≥ 18 and ≤ 85 years old
3. Specific aims 1 & 2 will include a subset of patients 10 years and < 18 years old with a firearm in the home.

Exclusion criteria:

1. Child is in an emergent/acute medical condition
2. Patient seen in our fast track area or other room without a television
3. Parent/guardian is non-English speaking.

For specific aims 1 and 2: Professional Research Assistants (PRAs) that staff the ED from 7am to midnight, 7 days per week will screen families, and approach any family with a child 10 years to < 18 years old to participate in a safety study. Caregivers who agree to participate will be asked to complete the first 10 questions of the baseline survey about child safety, including a question about firearm ownership and storage, on an iPad. Caregivers who answer the question "Are any of the guns in your home kept unlocked?" with "yes", "no", or "I don't know" will be included in the study. Those who answer "There are no guns in the home" will be excluded. Those included will complete the baseline survey.

For specific aims 3, 4 and 5: Professional Research Assistants (PRAs) that staff the ED from 7am to midnight, 7 days per week will screen families, and approach any family with a child 17 years or younger to watch a video about child safety. Caregivers who agree to participate will be asked to complete the first part of the baseline survey about child safety in general, including questions about firearm ownership and storage, on an iPad. Caregivers will then be randomized to watch either the 30-second or 3-minute Be SMART video. Following the video, caregivers will be asked to complete the second part of the baseline survey, also on an iPad, which will address acceptability of the video. In this part of the study, we will not restrict inclusion based on endorsed firearm ownership because it may be underreported, and we may miss messaging potential firearm owners. Additionally, the video includes

messaging about safe firearm behaviors that are more universally applicable, such as asking about firearms in other homes that children frequent.

C. Study Design and Research Methods

This will be an experimental pre-post pilot study performed in the ED at CHCO. Patients presenting to the ED with a non-emergent complaint will be screened by PRAs or the Principal Investigator and approached to participate after they are assigned an ED room and prior to leaving the room due to discharge, transfer or admission. Since this study is observational in nature, participation will not alter medical treatment or length of stay in the ED; therefore, after caregivers review a postcard consent about the study, they will be asked to answer a question in REDCap indicating if they agree to participate. If the child is of assenting age (7-17), we will have the child review a postcard assent about the study. They will then be asked to answer a question in REDCap indicating if they agree to participate. The postcard consent/assent will describe our goal as studying child safety in general and will not specifically refer to a firearm safety objective, in order to mitigate potential bias. We will debrief the caregiver about the minor deception after they complete the follow-up survey, as knowledge of study aims could bias answers to both the baseline and follow up survey.

Specific aims 1 and 2: To prevent potential contamination across providers in the ED, the intervention will only be given during one block of time. Families will be block randomized by date of presentation. In the first six months, or until we recruit the necessary number of participants, we will provide current standard of care with no new intervention – this will be group 1 (G1). In the following six months we will recruit into the intervention group – this will be group 2 (G2). In G1, parents will complete the baseline survey at time 0 (t0) and will complete the follow-up survey at 3 months (t3) via follow up phone call. In G2, parents will be asked to complete the baseline survey at t0 and will then be asked to watch the 3-minute Be SMART video. Parents in G2 will also complete the follow-up survey at t3 via follow up phone call.

Specific aims 3, 4 and 5: Those answer yes in REDCap indicating that they agree to participation will be randomized to watch either the 30-second or 3-minute Be SMART video. Each family enrolled will be asked to watch one of these two videos.

For all aims: The videos have been developed by “Be SMART” [17], an organization focused on responsible gun storage education and awareness. These videos describe safe firearm storage in the home, encourage parents to ask about firearm storage at homes their children frequent, and addresses removing firearms from the home if someone is having a mental health crisis. This messaging is applicable both to owners and non-owners of firearms. In addition, demographic information including subject’s name, age, sex, parents’ names, email addresses and telephone numbers will be collected. Clinical variables, such as presence or absence of mental health diagnoses, abuse, current presentation with mental health complaint, active suicidal or homicidal ideation and presentation with penetrating trauma, will also be collected from the electronic medical record (EMR) by the PI or other study investigators after the index visit.

Participants will be given a brief survey prior to the video to assess baseline storage habits along with other child safety behaviors. All families will also complete a survey immediately after the video to evaluate acceptability of the video. Participants will also receive a follow-up email or phone call to evaluate storage habits and firearm safety behaviors within 3 months after their visit. If we are unable to contact the family by email or phone, we will consider them a lost to follow-up (LTFU). For aims 1 and 2, we will give each family a \$5.00 gift card for participation in the study at the initial visit. For aims 3, 4

and 5, we will give each family up to a \$20 gift card for participation in the study - \$10 after watching the video and completing both parts of the baseline survey, and \$10 after completing the follow up survey.

Data from each subject will be entered into a REDCap database on a secure server. All identifiers will be removed from the data set after all participation is complete, including follow up, before data analysis. EMR review will occur after the index visit. Study investigators will manually review charts for descriptive and clinical characteristics. Each of these subjects' will already be registered in the secure REDCap database under a specific study number at the time of retrospective review and data will be entered here.

E. Description, Risks and Justification of Procedures and Data Collection Tools:

The study will consist of watching a brief video and responding to questions pertaining to pediatric safety. This intervention will not impact medical care or time spent in the ED in any way. Demographic characteristics to be recorded include age, sex, and race/ ethnicity of the child. Medical history and clinical variables will be collected such as presence or absence of mental health diagnoses, abuse, current presentation with mental health complaint, active suicidal or homicidal ideation and presentation with penetrating trauma.

The following measures will be taken in order to minimize the risk of breach of confidentiality that is always a concern with collection of protected health information (PHI). Each subject will be assigned a unique study number and all patient identifiers will be removed from the data set after participation is complete, including follow up, and before data analysis. All data including PHI will be stored in REDCap. (The UCD REDCap installation passed a rigorous 6-week security threat analysis performed by the UCD-Anschutz HIPAA Security Officer. All study data are stored on a secure database server which is separate from the web-facing server -- a best-practices for internet-based security. All user access requires user accounts and passwords. All user actions are recorded in a secure audit log. The database server is routinely backed-up. All security patches and application updates are applied immediately upon release by DISC.) Upon completion of the study, all patient identifiers in the data set will be removed.

F. Potential Scientific Problems:

The goal of this pilot study is to assess feasibility and acceptability of showing a firearm safety video in the ED, with the goal of a larger scale study to evaluate whether this video can improve storage practices and improve other firearm safety behaviors.

G. Data Analysis Plan:

We will collect demographic data from the patient's electronic medical record as well as survey results from the parent-completed survey.

Continuous variables will be described as means and standard deviations if normally distributed or median and interquartile range if non-normally distributed. Categorical variables will be described using counts and percentages. We will compare data between families who received the 30-second video and the 3-minute video using fisher exact tests, t-tests, or Wilcoxon rank sum tests as appropriate. All results will be presented in aggregate and performed in SAS (Cary, NC).

H. Summarize Knowledge to be Gained:

This study has the potential to utilize a novel approach to educating the public about safe firearm storage. If successful, it can improve rates of safe firearm storage where children and adolescents are living and increase safe firearm behaviors, thereby reducing morbidity and mortality caused by suicide, unintentional injuries, and assaults.

I. References

1. Runyan, C.W., et al., *Lethal Means Counseling for Parents of Youth Seeking Emergency Care for Suicidality*. West J Emerg Med, 2016. **17**(1): p. 8-14.
2. Cunningham, R.M., M.A. Walton, and P.M. Carter, *The Major Causes of Death in Children and Adolescents in the United States*. N Engl J Med, 2018. **379**(25): p. 2468-2475.
3. National Center for Health Statistics, C.f.D.C.a.P. *Stats of the State of Colorado*. April 13, 2018 [cited Sept 9 2019]; Available from: <https://www.cdc.gov/nchs/pressroom/states/colorado/colorado.htm>.
4. Pediatric Patient Education, A.A.o.P. *Firearms Injury Prevention*. [cited 2019 September 12]; Available from: <https://patiented.solutions.aap.org/handout.aspx?gbosid=166212>.
5. Grossman, D.C., et al., *Gun storage practices and risk of youth suicide and unintentional firearm injuries*. JAMA, 2005. **293**(6): p. 707-14.
6. Simon, O.R., et al., *Characteristics of impulsive suicide attempts and attempters*. Suicide Life Threat Behav, 2001. **32**(1 Suppl): p. 49-59.
7. Elnour, A.A. and J. Harrison, *Lethality of suicide methods*. Inj Prev, 2008. **14**(1): p. 39-45.
8. Spicer, R.S. and T.R. Miller, *Suicide acts in 8 states: incidence and case fatality rates by demographics and method*. Am J Public Health, 2000. **90**(12): p. 1885-91.
9. Azrael, D., et al., *Firearm Storage in Gun-Owning Households with Children: Results of a 2015 National Survey*. J Urban Health, 2018. **95**(3): p. 295-304.

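### Aim 1 counts removal of all guns as safe storage in a sample screened to exclude gun-free homes, so that component starts at zero and the stated before-after contrast cannot separate video-prompted removal from turnover or a changed answer

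*Combined protocol and SAP*

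**What the plan says.** Section I states Aim 1 as "measuring change in self-reported safe storage at baseline and 3 months after a brief ED intervention". Its hypothesis is "Safe storage counselling will improve safe storage practices by 15% over baseline rates". The outcome is to be judged "as measured by removing all guns from home or locking all guns and locking ammunition separately". A home thus meets the outcome by either of two routes, removal or locking.

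The entry criteria in section III.B tie these aims to gun-owning homes: "Specific aims 1 & 2 will include a subset of patients 10 years and < 18 years old with a firearm in the home". The screening rule for Aims 1 and 2 in the same section works on one question, whether any guns in the home are kept unlocked. Caregivers answering yes, no or that they do not know are enrolled. For the remaining answer, "Those who answer 'There are no guns in the home' will be excluded".

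Section III.A measures safe storage by self-report and gives example items on unlocked guns and on separate storage of bullets. No example concerns removal. The follow-up questionnaire is not part of the document.

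Section III.C describes two groups recruited in successive blocks of time: G1 with standard care and G2 with the 3-minute video. Both are surveyed at baseline and at 3 months. Section III.G names one comparison between groups, the 30-second against the 3-minute video. It names no G2 versus G1 comparison and no paired analysis, and it does not say how a no-guns answer at 3 months is scored.

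**The concern.** The screening answer that keeps a home out at baseline is also an answer that could show success at 3 months. Nobody enrolled can have given it at baseline, so the removal component can only rise. Homes that acquire guns after a gun-free start are never enrolled, so turnover in ownership enters this component in one direction only.

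A no-guns answer at 3 months can arise in at least three ways: the family moved the guns out because of the video; the guns left the home for unrelated reasons; or the answer changed while the guns did not. The third includes a caregiver who was enrolled after answering that they did not know and later learns that there are no guns. Only the first is an effect of the video. The stated before-after contrast credits all three to it.

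This matters because section I says the pilot's results will lead to an evaluation in a larger population, and Aim 1 is its evidence on behaviour.

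**Working it through.** The plan gives no sample size, planning rate or power for Aims 1 and 2, so there is no figure of its own to reproduce.

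**Inputs**
- Removal component at baseline: 0, from the screening rule in III.B.
- Baseline share storing safely, p: the plan gives no planning rate. Section II reports that firearms are "only safely stored in one third of homes with children", so p = 1/3 is used, with 20% to 50% as an assumed range.
- Share d of the homes not safe at baseline that answer no guns at 3 months for reasons other than the video: assumed. Nothing in the document supports a value.
- Target: a 15% improvement. Section I does not say whether this means percentage points or relative to baseline.

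**Before-after contrast.** If nothing else changes, the composite at 3 months is p + d(1 − p), so the gain is d(1 − p). Homes already safe at baseline add nothing.

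| p | gain at d = 5% | gain at d = 10% |
|---|---|---|
| 20% | 0.05 × 0.80 = 4.0 points | 0.10 × 0.80 = 8.0 points |
| 1/3 | 0.05 × 0.667 = 3.3 points | 0.10 × 0.667 = 6.7 points |
| 50% | 0.05 × 0.50 = 2.5 points | 0.10 × 0.50 = 5.0 points |

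**Against the target, p = 1/3.** Read as 15 points, the gains of 3.3 and 6.7 are 3.3/15 = 22% and 6.7/15 = 44% of it. Read as relative, the target is 0.15 × 33.3 = 5.0 points, and the same gains are 67% and 133% of it.

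**Switching needed to reach the target by this route alone.**
- Absolute reading, d = 0.15/(1 − p): 22.5% at p = 1/3 (18.8% at p = 20%, 30.0% at p = 50%).
- Relative reading, d = 0.15p/(1 − p): 7.5% at p = 1/3 (3.8% at p = 20%, 15.0% at p = 50%).

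**G2 versus G1.** With the same p in both groups, the difference in change due to such switching is (d2 − d1)(1 − p). If d is 5% in both groups, this is 0. If d is 5% in G1 and 10% in G2, it is 0.05 × 2/3 = 3.3 points, compared with 6.7 points in the before-after result for G2. The control group removes whatever is common to both periods and leaves only what differs between them.

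**The case against.** The restriction to gun-owning homes is deliberate: a home without guns has no storage to improve. Section III.C says the videos address taking firearms out of the home in a crisis, so real removal is rightly a success. G1 has the same entry rule and the same two surveys. The study is a pilot ahead of a planned randomised trial. All of this stands. It supports keeping removal in the outcome; it does not supply the missing G2 versus G1 analysis or a scoring rule.

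Several stronger readings are tempting, and the document does not support them.

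- A reader might infer that every later no-guns answer counts as improvement. For the composite this is false: a home that already locked guns and ammunition separately is safe at both times. The composite can also fall, if locked homes stop locking.
- A reader might infer that the screening rule inflates Aim 1 even when nothing changes. With stable behaviour and accurate answers, the change is zero. Turnover that empties a home of guns does meet the definition; the open question is what caused it.
- A reader might take the remark "we will not restrict inclusion based on endorsed firearm ownership because it may be underreported" as evidence that enrolled caregivers will later deny having guns. It explains why Aims 3 to 5 do not screen on ownership. Caregivers enrolled in Aims 1 and 2 did not deny guns at entry, and the remark says nothing about their answers at 3 months.
- A reader might infer that seeing a firearm video makes G2 caregivers less willing to disclose than G1 caregivers. This is possible but untested, and a caregiver wishing to look compliant could as easily claim that guns are locked.
- A reader might infer that removal can be seen only through a no-guns answer, or that a gun moved to the car would score as removed although the campaign message is "Secure all guns in your home and vehicle". The items in III.A are examples and the follow-up survey is not shown, so neither can be established.

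**Conclusion.** The concern holds in a limited form. The removal component is zero at baseline by selection, which follows directly from III.B. In the before-after contrast stated in section I, a 3-month no-guns answer from a home not safe at baseline counts as improvement whatever its cause. G1 would cancel turnover, provided turnover is alike in the two recruitment periods, but III.G does not use G1.

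The size is unknown. The illustrative 3.3 and 6.7 points rest on the background figure of one third safe and on assumed switching of 5% and 10%. How serious that is depends also on the reading of the target: switching alone would need to reach 22.5% of homes not safe at baseline on the absolute reading, but only 7.5% on the relative one. This is a cheap improvement worth making; it does not show that the Aim 1 result will be wrong.

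**What to change.** 1. At 3 months, ask each caregiver who reports no guns whether the guns present at the ED visit have been moved out since then and where they are now. Count removal when it is affirmed. The question on location also shows whether guns went to a vehicle.
2. Make the G2 minus G1 difference in change the Aim 1 contrast and add it to III.G.
3. Report the locked and removed components separately in G1 and G2, beside the composite.
4. State in advance how an unexplained switch to no guns is scored, including from caregivers who answered at baseline that they did not know. Show a sensitivity result with these switches scored the other way. Treating them all as failures in the main result is debatable, since some real removers may skip the item.
5. Add removal to the outcome description in III.A so that it matches the Aim 1 definition.

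The cost is one branching survey item and a few sentences of analysis plan. The reported improvement may be smaller, and the new item is itself self-report, so it reduces misclassification without eliminating it.

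### Section III.G states no analysis for Aims 1 and 2, and the wording elsewhere points to a change from baseline that would credit the intervention with any change also seen in the control group

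*Combined protocol and SAP*

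**What the plan says.** Section I words Aim 2 as an evaluation of effectiveness "by measuring parental knowledge at baseline and 3 months after a brief ED intervention". The Aim 1 hypothesis is that counselling will "improve safe storage practices by 15% over baseline rates". Section III.C begins: "This will be an experimental pre-post pilot study performed in the ED at CHCO".

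For these two aims, III.C sets up two groups. G1 receives standard care with nothing added, and completes the baseline survey at t0 and a telephone survey at t3. Then: "In the following six months we will recruit into the intervention group". Parents in that group, G2, "complete the baseline survey at t0 and will then be asked to watch the 3-minute Be SMART video", and have the same t3 survey.

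Section III.A lists three primary outcomes for Aims 1 and 2: safe storage (1), awareness that firearms can be transferred temporarily (2), and knowledge of a storage location or of the map link (3). Outcome 2 is a yes/no self-report. Its example item begins "Did you know that you can temporarily take your guns out of your home".

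Section III.G gives descriptive summaries and one comparison, between families shown the 30-second and the 3-minute video. It does not mention G1, G2, change from baseline, or Aims 1 and 2.

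**The concern.** The plan collects a control group for its two effectiveness aims but does not write down how that group enters the estimate. What it does write about those aims is change from baseline. An analyst who follows that wording would report G2's own change over three months as the effect. Any change that would have happened without the video is then counted as benefit: the effect of being surveyed, of the ED visit itself, or of events outside the hospital.

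Outcome 2 shows how this could happen, because the example item tells the respondent the fact it tests. A parent who answers no at t0 has just been informed, and can truthfully answer yes at t3 whatever the video did.

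At stake is whether the pilot's effectiveness estimates can be read as effects when they are used to justify and plan the larger study. Leaving the contrast open also lets it be chosen after the data are seen.

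**Working it through.** The plan gives no sample size, awareness rate, recall rate or effect size for Aim 2, so there is no figure of its own to reproduce.

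**1. Can the comparison in III.G serve Aims 1 and 2?** It needs families shown the 30-second video and families shown the 3-minute one. Under III.C, G1 sees neither and G2 sees only the 3-minute one. It cannot apply.

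**2. What does change from baseline estimate?** Write s for the change that occurs without the intervention and d for the intervention's added effect.

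- G2 change = s + d
- G1 change = s
- G2 minus G1 = d, provided s is the same in both groups

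For Aim 1, read the 15% as percentage points for illustration and assume s = 5. G2 then reaches 15 points over baseline with d = 15 − 5 = 10.

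**3. Outcome 2 with no video effect.** Every input is an assumption. Let b be the share aware at t0 and c the share of the unaware who retain the fact from the item until t3, and suppose nobody moves from aware to unaware. The rise in each group is (1 − b)c:

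| b | c = 5% | c = 20% | c = 40% | c = 60% |
|---|---|---|---|---|
| 10% | 4.5 | 18 | 36 | 54 |
| 30% | 3.5 | 14 | 28 | 42 |
| 50% | 2.5 | 10 | 20 | 30 |

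(Percentage points.) G2 minus G1 is 0 in every cell, by construction.

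**4. Outcome 2 with a real video effect.** Let v = 30% of otherwise unaware parents learn the fact from the video, independently of c, with b = 30%. The video alone adds v(1 − b) = 0.30 × 0.70 = 21 points.

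| | c = 5% | c = 20% | c = 40% | c = 60% |
|---|---|---|---|---|
| G2 rise, (1 − b)[1 − (1 − c)(1 − v)] | 23.45 | 30.8 | 40.6 | 50.4 |
| Excess over 21 | 2.45 | 9.8 | 19.6 | 29.4 |
| G2 minus G1, v(1 − b)(1 − c) | 19.95 | 16.8 | 12.6 | 8.4 |

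The pre-post rise overstates the video's own effect. G2 minus G1 understates it, by the fraction c.

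A simulation of the same model (4,000 runs, an assumed 100 per group) gave mean Mantel-Haenszel differences stratified by t0 answer of 0.0, −0.1, 0.1 and 0.0 with no effect, and 19.9, 16.9, 12.6 and 8.5 with v = 30%. This checks the estimator under the assumed model. It is not evidence about the trial.

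**5. Effect on a test.** Take b = 30%, c = 20% and no video effect. With changes in one direction only, an exact two-sided McNemar test in G2 gives p < 0.05 once six parents change (2 × 0.5^6 = 0.031; with five it is 0.0625). The chance of six or more at a 14% change rate is about 72% with 50 in the group and 99.7% with 100. A Fisher test of G1 against G2 at t3, both at 30 + 14 = 44%, gives p < 0.05 in 3.4% and 3.9%.

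**6. Price in precision.** Same case, assumed 100 per group:

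- G2 change: √(0.14 × 0.86/100) = 3.5 points standard error
- G2 minus G1, stratified by t0 answer, with about 70 unaware per group: 0.70 × √(2 × 0.20 × 0.80/70) = 4.7 points
- G2 minus G1, unadjusted: √(2 × 0.44 × 0.56/100) = 7.0 points

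Adjusting for the t0 answer recovers much of the lost precision, but not all of it.

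**The case against.** The strongest reply is that the comparison is obvious from the design. III.C separates the groups by period to avoid contamination and gives both the same two surveys. That arrangement has little purpose unless they are compared, and pre-post can describe a two-group design. This stands to a degree: a reader might infer that the control group has no planned use, and the documents do not support that. They support only that no analysis is stated. An implied contrast still leaves the estimate, the adjustment and the Aim 1 comparator open.

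The awareness example also rests on text nobody outside the study can see. The item is given only as an example, and the baseline topics listed in III.A (item 4c) and III.C do not name awareness. That it is asked at t0 is inferred from Aim 2's need for a baseline value. This objection stands, so the example is conditional and its size unknown. Outcome 3 is less exposed, because the item supplies neither a location nor a link.

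Two further inferences should be resisted. III.C remarks that "knowledge of study aims could bias answers to both the baseline and follow up survey". A reader might take this as the protocol conceding that the item teaches its own answer. It concerns the concealed firearm objective, which is a different mechanism. A reader might also conclude that comparing with G1 cures the item effect entirely. It removes the spurious rise when the video does nothing, but a real effect is still diluted (step 4), and sequential recruitment brings in calendar effects.

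**Conclusion.** The point holds. III.G states no analysis for Aims 1 and 2, and the surrounding wording points to change from baseline, which mixes the intervention's effect with any change shared with G1. That part rests on the text alone.

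The size cannot be fixed from the documents. For outcome 2, the assumed ranges give a spurious rise of 2.5 to 54 points, small when few parents retain the item and large when many do. This depends on the item being asked at t0 in wording like the example. For outcomes 1 and 3 the same logic applies to any shared change, again of unknown size.

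Pilot status and the control data already planned keep the consequences modest. It should still be corrected, because these aims claim to evaluate effectiveness.

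**What to change.** Add to III.G: *For Aims 1 and 2, effectiveness is estimated as the G2-minus-G1 difference in proportions at t3 with a 95% CI, adjusted for the t0 answer (for example, a Mantel-Haenszel risk difference stratified by t0 answer). Within-group changes are descriptive. Because G1 and G2 are recruited in consecutive periods, calendar effects may remain.*

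Restate the Aim 1 hypothesis as an improvement relative to G1 rather than to baseline alone.

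The cost is a few sentences and no new data, since both groups already have both surveys. Mantel-Haenszel is one acceptable adjustment among several. The plan should acknowledge three downsides: the consecutive periods leave calendar effects uncontrolled; any item effect common to both groups may dilute a true difference; and the between-group estimate is less precise than a within-group change.
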